6.2.2 Enrollment, Baseline, and Randomization

Enrollment

In this study, the enrollment date is the day the participant has met all the screening criteria and signs a single informed consent form that describes both screening and study procedures. RAs will record the enrollment date on a case report form along with the allowable window between screening and randomization.

Baseline Assessments

For participants who will have successfully been screened for eligibility and are enrolled in the study, baseline assessments will be performed to measure the study outcome on the same day of enrollment. We will measure study outcomes as listed below:

Anxiety and Depressive Symptoms

The Hopkins Symptom Checklist-25 (HSCL-25)² will be used to measure anxiety and depressive symptoms² experienced over the past month. It is composed of a 10-item subscale for anxiety and a 15-item subscale for depression, with each item scored on a Likert scale from 1 (not at all) to 4 (extremely). The scale was validated for use in Nepal with a clinical DSM-IV diagnosis of major depressive disorder. The sensitivity and specificity with a cutoff point of 1.75 were 0.87 and 0.60, respectively, with an area under the curve of 0.79.⁵⁰ The HSCL-25 has widely been used in studies among refugees in other countries as well as Nepal. The HSCL-25 score was categorized into two groups: the cutoff score of 1.75, depressed (1.75 or more), and not depressed (below 1.75). The scale has high internal consistency for anxiety (Cronbach's $\alpha = 0.92$) and depression (Cronbach's $\alpha = 0.94$) in our previous Bhutanese study.³⁹

Perceived Stress

The 10-item Cohen Perceived Stress Scale (PSS)¹ will be used to assess perceived stress. The PSS uses a 5-point Likert scale (ranging from 0, “never” to 4, “very often”) to assess psychological stress experienced during the past month, including

the extent to which situations felt unpredictable, uncomfortable, and overwhelming. The items included in the PSS scale are easy to understand as it was designed for use with community samples with junior high school education. This scale has been widely used in different populations, including immigrants. The scale has high internal consistency (Cronbach's $\alpha = 0.80$) in our previous Bhutanese study.³⁹ Items were summed to provide a total score with higher scores indicating greater perceived stress.

Physiological stress

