We will use the ELISA cortisol hair-test (average hormone levels over the past three months) as a biomarker to measure physiological stress. Neuroendocrine indicators, such as cortisol, are effective stress biomarkers because they are the first to respond to a given stressor and coordinate the physiological response of other bio-physiological systems. Biomarker measurement helps overcome the limitations of self-report because it provides an objective marker of stress levels. Hair samples will be processed in the neuroendocrine lab at UMass.^{51, 52} Sensitive and specific enzyme immunoassay (Salmetrics) will be used for the analysis. The assay has intra- and inter-assay coefficients of variation of <10%. The cortisol distribution will be tested for normality, and if the data are not normal, they will be log-transformed before statistical analysis.

Coping strategy

Coping strategy⁵⁴ will be measured using a 32-item Coping Strategies Inventory-Short Form (CSI-SF). The CSI-SF includes two overall coping factors, Engagement and Disengagement, and four secondary factors, Problem Engagement, Problem Disengagement, Emotion Engagement, and Emotion Disengagement. The CSI-SF scale (Cronbach's $\alpha = 0.95$) and its subscales problem engagement (Cronbach's $\alpha = 0.87$), emotion engagement (Cronbach's $\alpha = 0.89$), problem disengagement (Cronbach's $\alpha = 0.81$), and emotion disengagement (Cronbach's $\alpha = 0.78$) have high internal consistencies in our previous Bhutanese study.³⁹ A sample item for this scale is, "I worked on solving the problems in the situation." Participants were asked to rate

their responses on a 5-point Likert-type scale ranging from *not at all (1)* to *very much (5)*. Items are summed to provide sub-scale and larger composite scores with higher scores associated with greater adherence to that coping style.

Self-efficacy

Self-efficacy will be measured using a 26-item Coping Self-efficacy(CSE)⁵⁵ scale for coping with challenges and threats. A sample item for this scale is “Do something positive for yourself when you are feeling discouraged.” Each item of the scale will be rated on an 11-point scale Likert-type scale ranging from *(0) cannot do at all, (5) moderately certain can do, and (10) certain can do*. Graded items will be summed up to provide a total score, and higher scores indicate high self-efficacy. The scale has high internal consistency (Cronbach’s $\alpha = 0.96$) in our previous Bhutanese study.³⁹

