9 STATISTICAL CONSIDERATIONS

9.1 Sample Size and Randomization

The pilot project aims to estimate the magnitude of the difference between the preventive intervention and the education control on the primary outcomes of interest (stress, anxiety, depressive symptoms) to inform the design of a large-scale intervention. A study comparing PMP to a treatment-as-usual control in Pakistan⁶¹ found a mean difference of about 7 points with a standard deviation of 8.5 on a measure of anxiety and depression for effect size ($ES=.86$). We do not expect our ES to be as large as what was observed in the Pakistani study⁶¹ given that we are doing a prevention trial and not an intervention study in a distressed population so that this study will provide an estimate of the ES of PMP as a preventive intervention.

We conducted a power analysis to detect an ES as small as $ES=.30$ with $\alpha = .05$ and power of $.80$. We may find a larger effect in our pilot, but our understanding is that power estimates should be based on the smallest effect that we want to detect rather than the size of the effect that we expect.⁶² We expect that families will average approximately 2-4 adult persons based on our pilot data, and conducted our power analysis to account for the correlation among family members. Analyses were conducted using Optimal Design,⁶³ which is power analysis software created for cluster randomized trials such as the present study. Accounting for the intra-correlation among family members of $.10$ and $\alpha = .05$, we would have 80% power to detect a standardized difference of $ES=.30$ between two treatment groups of 116 families (58 per treatment arm) with an equal probability of being randomized to each of our two intervention arms.

As noted above, we do not expect our ES to be as large as in the Pakistani study, but a sample of that size should be sufficient to provide the estimates of the differences between the conditions (with standard deviation in our sample) and the correlations between the targets specified by theory and our primary outcome of interest to inform the design of a larger-scale controlled trial. The other goal for the project is to determine whether the intervention affects the target mechanisms specified by theory to mediate or moderate the intervention's impact on the outcomes. Those estimates we will get from the correlation between our respective targets (coping and self-efficacy) and the primary outcomes.

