content analysis.⁵³ Feedback provided by the field staff will be reviewed and coded to identify recurrent themes regarding the intervention's acceptability. All analyses will be conducted in the Nepali and translated into English. Fidelity data will be used to assess intervention content and transmission. We will determine retention by obtaining proportions of participants attending all or portion of sessions.

Aim 2b Intervention efficacy: We will carry out data management and descriptive analyses for study outcomes. Means, standard deviations, and percentile distributions will be used to describe the continuous baseline variables. Frequencies and percentages will be used to describe categorical variables. We will compare baseline characteristics of intervention and control groups using chi-square and t-tests as appropriate. While differences between groups are not expected because of the randomization used in the study design, variables showing significant differences between the two groups will be included as covariates in primary analyses. We will compare participants' characteristics to follow-up to those with complete data to assess potential limitations in recruitment and retention.

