Figure 1 provides a visual representation of our proposed analyses, in which treatment is a predictor of treatment targets or mechanisms (i.e. the mediators such as coping), which are in turn associated with outcomes. As reviewers 1 and 3 note, in mediational analyses, variables must be measured in *temporal sequence*.

Figure 2 provides a visual representation of our proposed temporal sequence of variable measurement for mediational analyses, in which treatment randomization occurs before mediator target measurement, which in turn are collected before the outcome measure used in the proposed analyses. Second, it is crucial to test the *indirect effect* (a*b paths) of the treatment on the outcome through the hypothesized mediators. As the indirect

effect is not normally distributed, we will assess its significance via Monte Carlo simulated confidence intervals, which are the recommended counterpart in multilevel mediation to bootstrapped confidence intervals used in single-level analyses.⁶⁶⁻⁶⁸

Each potential mediational sequence will be tested in this manner (see **Table 1** for mediators and outcomes to be tested). While we acknowledge that mediational analyses are difficult to adequately power in a sample of our proposed size,⁶⁷ we believe these preliminary analyses will help identify potential mechanisms for our treatment effect. If baseline differences in treatment groups are found in either the mediating or outcome variables, baseline measures will be controlled for in all analyses. Sample mixed-format multilevel equations are provided below, where the nesting of measures (i) within families (j) is accounted for by the random effects u_{0js} : γ_{01} in the Mediator equation is the ‘a path’, and γ_{10} in the Outcome equation is the ‘b path.’

Table 1 Mediators and Outcome Variables

Mediators (Targets)	Outcomes
Coping, Self-Efficacy	Perceived Stress
Family or Social Support	Physiological Stress
Family Conflict Resolution	Anxiety Symptoms
Family Satisfaction	Depressive Symptoms
Family or Social Network	

$$T2Mediator_{ij} = \gamma_{00_Med} + \gamma_{01_Med} * TreatmentCondition_j + u_{0j_Med} + r_{ij_Med}$$

$$T3Outcome_{ij} = \gamma_{00_Out} + \gamma_{10_Out} * T2Mediator_{ij} + \gamma_{01_Out} * TreatmentCondition_j + u_{0j_Out} + r_{ij_Out}$$

The key estimates are the association of the treatment condition with the mediator (γ_{01_Med} , a path) and the association of the T2 mediator with the T3 Outcome (γ_{10_Out} , b path).

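### The mediation models adjust for baseline mediator and outcome only when the arms differ at baseline, a trigger that does not address confounding of the mediator-to-outcome path

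*Combined protocol and SAP*

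**What the plan says.** Section 9.2 (Aim 2c) tests the product of two paths with a Monte Carlo confidence interval: treatment to T2 mediator (a), and "the association of the T2 mediator with the T3 Outcome" (b). Its rule for baseline adjustment is: "If baseline differences in treatment groups are found in either the mediating or outcome variables, baseline measures will be controlled for in all analyses". It gives no threshold for a difference and does not say which variables count. The sample outcome equation contains an intercept, the T2 mediator, treatment, a family effect and a residual, with no baseline term. The only causal safeguard described is the time order of the measurements.

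The Aim 2b rule is similar ("variables showing significant differences between the two groups will be included as covariates in primary analyses") but covers only the primary analyses. Nowhere is baseline adjustment of the mediation models made unconditional, and no assumption about mediator-outcome confounding is stated.

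Section 9.2 says of the mediation work that "we believe these preliminary analyses will help identify potential mechanisms for our treatment effect". On target mechanisms, section 9.1 says: "Those estimates we will get from the correlation between our respective targets (coping and self-efficacy) and the primary outcomes".

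**The concern.** Randomisation makes the arms comparable, so the a path is protected. Nobody randomises T2 coping or self-efficacy. A participant who starts with poor coping and high distress tends to remain so. T2 mediator and T3 outcome are then associated within each arm for reasons unrelated to any mediator effect. A comparison between arms cannot see this, because the bias is at full size when the arms are perfectly balanced. Measuring the mediator before the outcome does not remove causes that precede both.

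Two errors can follow. A mediator that PMP-I moves but that has no effect on the outcome can appear to mediate. Where the true effect and the baseline correlation have opposite signs, real mediation can be hidden. The sign may differ between mediators. Section 6.2.2 notes that "The CSI-SF includes two overall coping factors, Engagement and Disengagement", with higher scores meaning more of that style in each case.

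Because the trigger is undefined, the choice of model is also left open until the data have been seen.

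**Working it through.** The plan states no power, correlation or effect size for the mediation analysis, so there is no figure of its own to reproduce.

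**Inputs from the documents.** 58 families per arm and family ICC .10 (9.1); 226 adults (synopsis). To reach 226, each arm has 55 families of two and 3 of one: 2 × (55×2 + 3) = 226.

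**Assumed inputs.** Baseline mediator-outcome correlation rho; stability s, taken equal for mediator and outcome; effect a of PMP-I on the mediator, .3 or .5 SD; trigger at p<.05 by individual-level t-test, borrowed from the Aim 2b rule.

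**Bias.** With unit variances, M2 = s·M0 + a·T + e1 and Y3 = s·Y0 + b·M2 + e2. When b = 0, the within-arm covariance of M2 and Y3 is s·s·rho, so the unadjusted b is shifted by rho·s²:
- .2 × .5² = .050
- .3 × .5² = .075
- .4 × .6² = .144
- .5 × .7² = .245

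The shift takes the sign of rho.

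**How often the trigger fires under valid randomisation.**
- One mediator-outcome pair: 1 − .95² = 9.75% (simulated 10–12%).
- Any of the 10 Table 1 variables (6 mediators, 4 outcomes): 1 − .95¹⁰ = 40.1% (simulated 46–48%).
- Any of 17, if subscales count: 1 − .95¹⁷ = 58.2% (simulated 65–67%).

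The simulated rates are higher because the t-test ignores families. Correlation among the variables would lower the last two.

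**False mediation, true b = 0, a = .3 SD.** Both equations were fitted with a family random intercept and a Monte Carlo interval for a·b, 3,000 runs per cell. Entries are the % of intervals excluding zero:

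| rho / s (absolute) | Never adjusted | Pair trigger | Any of 10 | Any of 17 | Always adjusted |
|---|---|---|---|---|---|
| .2 / .5 | 5.6 | 5.4 | 4.3 | 3.4 | 2.6 |
| .3 / .5 | 9.9 | 9.4 | 7.3 | 6.0 | 3.3 |
| .4 / .6 | 31.1 | 27.7 | 17.2 | 12.3 | 3.3 |
| .5 / .7 | 55.2 | 49.7 | 32.2 | 22.2 | 4.1 |

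At a = .5 the pair trigger gives 10.3 / 16.6 / 50.0 / 82.4%, any of 10 gives 8.8 / 12.0 / 32.7 / 51.8%, and always adjusting gives 5.3 / 4.9 / 5.2 / 5.6%. The mean unadjusted b matched rho·s² within .002, and the mean adjusted b was within .002 of zero. With rho = 0 and a = .5 there is no excess (4.9% against 5.2%). With a = 0 the rate stays at or below about 6%, so false mediation needs a treatment effect on the mediator.

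**Masking, true b = −.2, rho positive, a = .3.** Mediation is detected in 35.5 / 28.9 / 13.8 / 8.1% under the pair trigger, against 55.9 / 55.9 / 61.5 / 68.7% always adjusted. A separate run of the any-of-10 reading (600 runs per cell) gave 45 / 39 / 29 / 34% against 57 / 55 / 59 / 70%.

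**Limits of adjustment.** In the .4/.6 case at a = .3, a residual correlation of ±.1 or ±.2 arising after baseline leaves 23–24% or 61–63% false mediation even when always adjusted. The pair trigger gives 44.3% or 55.4% when that residual has the sign of rho. When the signs are opposite the biases partly cancel, and it gives 11.7% or 9.8%.

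**The case against.** The strongest points on the other side are these.

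- **The sentence does not forbid further adjustment, and the equations are labelled as samples.** True, but it is the only adjustment rule given for these models, and nothing else supplies an unconditional one.
- **The pair reading is unfavourable to the plan.** The sentence can equally mean that an imbalance in any listed variable triggers adjustment everywhere. That lowers the rates at a = .3 to 4–32% (10 variables) or 3–22% (17 variables). Bias remains whenever the trigger does not fire.
- **The sizes are assumed.** This stands. In the mildest case at a = .3 there is no excess over 5%. Excluding participants with PHQ-9 scores of 15 or above (4.1, 4.2) narrows the symptom range and may point towards the milder cases. Missing T2 or T3 data, not simulated, would also lower the rates. In the other direction, three adults per family (N = 348) raises the pair-trigger rates at a = .3 to 9.1 / 16.5 / 46.1 / 63.4%.
- **Masking is more speculative than false mediation.** It needs a true effect opposite in sign to the baseline correlation, and the documents do not show that this occurs.
- **Adjustment is not a cure, and with opposite-sign residual confounding it can do worse than the trigger.** This stands, and is why the plan should state the limit. It does not make between-arm imbalance a sensible trigger.
- **The analysis is preliminary and its limited power is admitted.** This stands and limits the severity. Low power does not excuse a bias that the plan's own baseline data can reduce.

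**Conclusion.** The concern holds. The trigger looks for differences between arms, while the confounding lies within arms, so the b path stays biased by rho·s² whenever the trigger does not fire. That conclusion does not depend on the simulated values.

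The size does. Over the assumed range at a = .3 SD, false mediation runs from no excess over 5% to about 50% under the pair reading, and to about 32% or 22% under the broader readings, against 3–4% with both baselines always included. These figures assume N = 226, ICC .10, a p<.05 trigger, complete data, and baseline mediator and outcome as the only confounders.

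The change should be made because it is nearly free and these analyses are meant to inform mechanisms for a larger trial. No primary or secondary outcome test is affected.

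**What to change.** In section 9.2 (Aim 2c), replace the conditional sentence with wording such as: *The outcome equation will always include the baseline (T1) value of the mediator and of the outcome, whatever the baseline comparison shows; the mediator equation will include them for precision.* Add both T1 terms to the sample equations.

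In section 9.1, refer to this adjusted b path for the mechanism estimates. Raw target-outcome correlations can still be reported as descriptive planning quantities.

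State that the adjustment addresses confounding through the measured T1 mediator and outcome, and that common causes arising after baseline may remain. If a sensitivity analysis is reported, use a grid of residual correlations between the two equations that is symmetric about zero (for example −.2, −.1, 0, .1, .2), or sign it in advance for each mediator-outcome pair. Report the value at which a·b reaches zero.

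The cost is SAP wording, two covariates per model and slightly more analysis work. No new data are needed: section 6.2.2 says "baseline assessments will be performed to measure the study outcome on the same day of enrollment" and lists the mediator scales, the outcome scales and hair cortisol there. Because hair samples may be missing (section 10.2.5 has a deviation code for this), the plan should also say how a missing baseline covariate will be handled.

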10 DATA COLLECTION AND QUALITY ASSURANCE

10.1 Data Collection Forms

10.1.1 Survey Questionnaire: Trained community research assistants will collect information from participants using attached screening and survey questionnaires and instruction sheets to measure blood pressure, body weight, height, and waist circumferences, and hair samples collection. PI will provide two full days of training to RAs on all aspects of the study procedure, including recruitment procedure, informed consent, screening, pre, and post-assessment survey tools using a questionnaire, anthropometric and blood pressure measurement, hair sample collection and storage procedure, logistics materials, and administrative details. Training sessions include document review, role-play, and practice exercises. We plan to recruit the RAs who worked in our pilot studies to conduct surveys, measure anthropometric parameters and blood pressure, and collect hair samples. The quality of their data collection was excellent in our previous baseline and pilot intervention studies. RAs will complete required human subject research training, including the Collaborative Institutional Training Initiative (CITI) and Good Clinical Practice (GCP).

10.1.2 Screening tool: Trained RAs will use the Patient Health Questionnaire (PHQ-9), a screening questionnaire for depression, to screen the study participants and record each screened participant in the screening log.

10.1.3 Survey questionnaire: Trained RAs will use the survey questionnaire, including various validated scales to measure stress, anxiety and depressive symptoms, coping, social support, social networking, family conflict resolution, and family satisfaction to collect information from the participants at baseline, post-intervention, and 3-month post-intervention. These tools have high internal consistency among the Bhutanese population in our pilot studies (Cronbach's alpha range 0.78 – 0.94).³⁹

10.1.4 Body measures: Trained RAs will follow standard procedures mentioned in the “Training Manual for Research Assistant” to measure blood pressure, body weight, height, and waist circumferences of study participants.

10.1.5 Hair samples collection: Trained RAs will follow standard procedures mentioned in the “Training Manual for Research Assistant” to collect hair samples of study participants for the stress biomarker measurement. Hair samples will be cut from the posterior vertex of the scalp, carefully placed in aluminum foil, and stored at room temperature until delivery to [name] laboratory at the University of Massachusetts Amherst. Each sample will be cut to a length of 3 cm (if available) from the root (scalp) end and then processed into the [name] laboratory. Briefly, cut samples will be washed twice in 1 ml of isopropanol to remove external contaminants, including cortisol deposited on the outside of the hair shaft from sweat and sebum. After drying overnight, samples will be ground to be fine powder using a bead mill. 1.5 ml of methanol will be added to each sample, after which the samples will be subjected to slow rotation for 18-24 hours to extract the cortisol. 1.0 ml of the extract will be transferred to a clean tube, dried down using a vacuum evaporator, and then reconstituted in 0.25 ml of assay buffer. Reconstituted extracts will be spin-filtered to remove any residual particulate matter and then frozen at -20C for later assay. The cortisol content of each sample will be analyzed in duplicate along with standards and quality controls using the Arbor Assays commercial ELISA kit. Finally, the assay readout will be converted to pg cortisol per mg hair weight.

10.1.6 Confidentiality of participants’ information and record: All interviews will be conducted with the utmost privacy and confidentiality. Each interested adult participant in the family will be interviewed individually, in a private place where they feel comfortable, by our trained community RAs who have worked with the PI in previous intervention studies. The RAs will ensure audio and visual privacy at these sites and ensure data confidentiality. The RAs will assure each participant that their information will be kept confidential and not shared with anybody, including family members, in any context. Moreover, community interventionists will present the PMP-I interventions in family settings welcoming the participation of all interested family members, including parents

and young (<18 years) and old children (aged 18 years and above), without revealing individual participant's data and mental health status.

Furthermore, the RAs will explain the confidentiality procedure in detail before collecting any data. The RA will share the following guidelines to maintain subject privacy: we will use a numeric code in place of names in all records to ensure confidentiality. The survey materials will be stored in a locked cabinet in the PI's office. Only the PI will have access to the cabinet's key. Data entry will be performed on the PI's office computer (encrypted and password protected) under the full supervision of the PI. All original data will be kept in Box, a secure, networked UMass Amherst data storage system. Study folders will only be accessible by the PI and through the secure on-campus network. De-identified data sets will be used for statistical analyses. Summary data and analysis results will be stored on the PI's UMass office computer or the Box network. The PI herself will do data analysis and documentation.

Data will only be presented in aggregate form in manuscripts or conference abstracts, and no individual respondent will be identified. The questionnaires, transcriptions, and field notes will be kept separate from identifying informed consent and ID information. The master list of participants will be kept under a locked cabinet with access limited to the PI.

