Anxiety and Depressive symptoms: The Hopkins Symptom Checklist-25 (HSCL-25)² will be used to measure anxiety and depressive symptoms experienced over the past month at baseline, post-intervention, and three-month post-intervention. It is composed of a 10-item subscale for anxiety and a 15-item subscale for depression, with each item scored on a Likert scale from 1 (not at all) to 4 (extremely).

Secondary outcome

Physiological stress: Cortisol hair-test (average hormone levels over the past three months) will be used as a biomarker to measure physiological stress. Neuroendocrine indicators, such as cortisol, are effective stress biomarkers because they are the first to respond to a given stressor and coordinate the physiological response of other bio-physiological systems.

Interventions and Duration

Study Arms:

Experimental: Problem Management Plus for Immigrants (PMP-I) at family settings

Active Comparator: Talk program with Community Support Service Pamphlet (CSS)

Assessment:

Baseline, Post-Intervention, and 3-month Post-Intervention

Intervention:

PMP-I is a 5-week, peer-led, culturally tailored psychoeducation, behavioral activation, and problem-solving (90 minutes), breathing and yoga intervention (90 minutes) in a family setting. PMP-I will use a structured approach, including once a week, face-to-face sessions, breathing, yoga practice, homework that includes recording activities, rebuilding individual skills, or learning new skills to reduce stress.

- 1. Managing Stress:** Breathing and yoga practices, stress-management sessions, and behavioral activation exercises to strengthen positive coping strategies.
- 2. Managing Problems:** Practice exercises to identify the problems, develop solutions, and plan a strategy to carry out those solutions.
- 3. Behavior Activation:** Communication skill sessions and practice exercises to identify and carry out pleasant tasks.
- 4. Strengthening Social Support:** Social skills session and practice exercise to identify social support.
- 5. Staying Well:** Make a plan that helps to create a supportive family environment.

Sample Size and Population

This study will be conducted among 226 Bhutanese adults settled in Massachusetts.

STUDY TEAM ROSTER

Principal Investigator: [name]., MPH, MPHC, CGM
Assistant Professor, College of Nursing, [name], University Massachusetts Amherst, MA, 01003
Email: [contact]
[contact]

Co-Investigator: [name].

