Brief Description: We will use the ELISA cortisol hair-test (average hormone levels over the past three months) as a biomarker to measure physiological stress. Neuroendocrine indicators, such as cortisol, are effective stress biomarkers because they are the first to respond to a given stressor and coordinate the physiological response of other bio-physiological systems. Biomarker measurement helps to overcome the limitations of self-report because it provides an objective marker of levels of stress. Hair samples will be processed in the neuroendocrine lab at UMass.^{51, 52} Sensitive and specific

enzyme immunoassay (Salmetrics) will be used for the analysis. The assay has intra- and inter-assay coefficients of variation of <10%. The cortisol distribution will be tested for normality, and if the data are not normal, they will be log-transformed before statistical analysis.

Study Location and Population:

Bhutanese adults resettled in Massachusetts, USA.

Study Arms:

Experimental: Problem Management Plus for Immigrants (PMP-I) at family settings (58 families)

Active Comparator: Talk program with Community Support Service Pamphlet (CSS) (58 families)

Intervention:

PMP-I is a 5-week, peer-led, culturally tailored psychoeducation, behavioral activation (90 minutes), breathing, and yoga intervention (90 minutes) in a family setting. PMP-I will use a structured approach, including a once-a-week face-to-face session, breathing, and yoga practices.

1. Managing Stress: Breathing and yoga practices, stress-management sessions, and behavioral activation exercises to strengthen positive coping strategies.

2. Managing Problems: Practice exercises to identify the problems, develop solutions, and plan a strategy to carry out those solutions.

3. Behavior Activation: Communication skill sessions and practice exercises to identify and carry out pleasant tasks.

4. Strengthening Social Support: Social skills session and practice exercise to identify some support.

5. Staying Well: Make a plan that helps to create a supportive family environment.

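### Hair under 3 cm has no visible minimum, recorded length or analysis rule, yet every cortisol value is labelled a three-month average; the named assay also differs between sections

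*Combined protocol and SAP*

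**What the plan says.** Hair is collected at baseline and at the final visit, Day 132 (Sections 3, 6.1 and 6.2.4).

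- **Length.** Section 10.1.5: "Each sample will be cut to a length of 3 cm (if available) from the root (scalp) end". The text sets no lower limit and does not say what happens to shorter hair.
- **Label.** Section 6.2.2: "We will use the ELISA cortisol hair-test (average hormone levels over the past three months) as a biomarker to measure physiological stress". Section 3 and the opening summary describe the outcome in the same way. None of the three makes an exception for short hair.
- **Data handling.** Results are expressed in pg per mg of hair (Section 10.1.5). Sections 3 and 6.2.2 plan a normality check and, if needed, a log transform. The only hair item among the deviation codes in Section 10.2.5 is a missing sample.
- **Assay.** Section 6.2.2 states: "Sensitive and specific enzyme immunoassay (Salmetrics) will be used for the analysis". Its next sentence gives intra- and inter-assay CVs below 10%, and Section 3 says the same. Section 10.1.5 instead has each sample analysed in duplicate "using the Arbor Assays commercial ELISA kit" and gives no CVs.

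**The concern.** A length that depends on what the participant has, combined with a fixed time label, means that values from people with under 3 cm of hair describe a shorter period than the label says. Expressing cortisol per mg corrects for the amount of hair, not for the time it covers. If the length is not written down, the analyst cannot later tell which window a value represents.

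This matters somewhat more than usual for a secondary outcome. The trial is unmasked and its primary outcomes are self-reported. Section 3 justifies cortisol as the objective counterpart to self-report. It is also an outcome in the mediation analyses (Section 9.2, Table 1). Section 9.2 gives the ultimate goal as an effect size for each outcome to plan a full-scale trial, so the cortisol SD is something the pilot is meant to deliver.

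The two assay names raise a separate and simpler problem: the quoted precision may belong to a kit that is not used.

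**Working it through.** The plan gives no figure to reproduce here. The check has three parts.

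**1. Time windows.** Inputs: 3 cm (Section 10.1.5), three months (Sections 3 and 6.2.2), sampling at Day 0 and Day 132 (Section 6.1). The documents state no growth rate; pairing 3 cm with three months implies 1 cm per month, taken as 30 days. Window in days = length in cm × 30, counted back from sampling.

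| Length | Days covered | Window at baseline | Window at final visit | Share of 90 days |
|---|---|---|---|---|
| 3 cm | 90 | −90 to 0 | 42 to 132 | 100% |
| 2 cm | 60 | −60 to 0 | 72 to 132 | 67% |
| 1.5 cm | 45 | −45 to 0 | 87 to 132 | 50% |
| 1 cm | 30 | −30 to 0 | 102 to 132 | 33% |

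A full 3 cm sample at the final visit begins at Day 42, the post-intervention visit. A 1 cm sample misses the first two of those three months. Someone with 3 cm at one visit and 1 cm at the other is compared over 90 days against 30.

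**2. Illustrative size.** The documents give neither the month-to-month correlation r nor the share p with short hair, so both are assumed. Take equal monthly variances and the same correlation between any two months.

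- Var(3-month mean) ÷ Var(1 month) = (1 + 2r)/3. At r = 0.5 this is 0.667; at r = 0.8 it is 0.867.
- A 1 cm value therefore has k = 3/(1 + 2r) times the variance of a 3 cm value: 1.50 at r = 0.5 and 1.154 at r = 0.8.
- Its correlation with the three-month mean, before assay error, is √((1 + 2r)/3): 0.82 and 0.93.
- If a share p has 1 cm and the rest 3 cm, with the same mean and the same treatment effect, the pooled variance relative to all-3 cm samples is 1 + p(k − 1). The standardised effect is multiplied by 1/√(that ratio), and the sample size of a trial planned on it rises in proportion to the ratio.

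| r | p | Variance ratio | Fall in standardised effect | Rise in next trial's sample size |
|---|---|---|---|---|
| 0.8 | 10% | 1.015 | 0.8% | 1.5% |
| 0.8 | 50% | 1.077 | 3.6% | 7.7% |
| 0.5 | 10% | 1.050 | 2.4% | 5% |
| 0.5 | 50% | 1.250 | 10.6% | 25% |

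Assay error of equal size at both lengths would shrink these figures.

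**3. Assay names side by side.** Sections 3 and 6.2.2: Salmetrics, CVs below 10%. Section 10.1.5: Arbor Assays, no CVs. They name different sources for one measurement. No section allocates kits by person, arm or visit. A between-kit shift cannot be computed, since no conversion is given, and nothing suggests one is needed.

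**The case against.** Several points against this are sound.

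- **Silence is not permission.** Hair collection also follows a training manual (Section 10.1.5), instruction sheets (Section 10.1.1) and a compliance checklist (Sections 5.2 and 9.2), none of which is in the documents. A reader might infer that hair of any length is accepted and its length never recorded. The documents support only that no such rule is visible in them. Even so, field forms would not normally supply the missing analysis rule, nor settle which kit is used.
- **Two names are not two kits.** A reader might infer that values shift between people or between a person's two visits because the kit changes. Section 10.1.5 as written puts each sample on a single named kit, with standards and quality controls. The conflict is one to reconcile. What remains open is that the text does not say whether a person's two samples share a run.
- **The values are not incomparable.** On the assumptions above, a 1 cm value still correlates 0.82 to 0.93 with the three-month mean, and people with 3 cm at both visits are unaffected.
- **The consequence is limited.** Randomisation should balance hair length across arms, so no arm bias is expected. Cortisol is secondary in a pilot, and Section 9.2 makes the endpoint difference the key test, with change over time not powered.
- **Restricting to 3 cm samples selects people.** Length at Day 132 is also known only after randomisation. Both stand, so that analysis is a sensitivity check and should not replace the main one.

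**Conclusion.** The point holds as a modest, inexpensive improvement. Followed as written, the plan can pool different exposure windows under one label, with no length shown in the documents that would separate them later. The effect is added noise and a mixed definition of the outcome for people with under 3 cm of hair, not expected bias between arms. Its size is unknown; the illustrative range is a variance increase of about 1.5% to 25%. That range rests on an implied 1 cm per month, an assumed r of 0.5 to 0.8, an assumed 10% to 50% of participants with exactly 1 cm, and a treatment effect that does not depend on the window.

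The assay conflict is a plain contradiction about which kit the precision figures describe. It does not show that two kits will be used.

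**What to change.** 1. In Section 10.1.5 and on the collection form, record the assayed length in cm at both visits.
2. In Section 9.2, include length at the analysed visit as a covariate in the cortisol model. This assumes that the programme does not itself alter hair length. Add a sensitivity analysis restricted to 3 cm samples, stating that this subset is selected. Reserve the description as a three-month average for 3 cm samples.
3. Name one kit in Sections 3, 6.2.2 and 10.1.5, with that kit's own CVs.
4. Extracts are already frozen for later assay, so run each person's baseline and Day 132 extracts on the same plate, with both arms on every plate.

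Trimming Day 132 hair to match a shorter baseline sample is tempting but should not be done. It would turn a valid Day 42 to 132 sample into, for example, a Day 102 to 132 one at the key endpoint. It would also do nothing for people whose Day 132 hair is the shorter of the two.

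The cost is one form field, one covariate, one sensitivity run, some laboratory scheduling, and baseline cortisol results that arrive only once the Day 132 extracts are ready.
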